- 6. von Ungern-Sternberg, Effect of obesity and site of surgery on perioperative lung volumes. British Journal of Anaesthesia , Volume 92 , Issue 2 , 202 207.
- 7. https://clinicaltrials.gov/ct2/show/NCT02865083?term=pannus+retraction&rank=1

B3. DESCRIPTION OF RESEARCH PROTOCOL A. Study Design – Overview, Methods, Procedures

Overview

To determine whether the traxi® device warrants incorporation into routine practice, we will conduct an open-label, randomized, controlled trial to evaluate the use of traxi for obese patients undergoing non-urgent cesarean delivery. We will examine operative time, cardiopulmonary function, and patient/provider satisfaction.

Methods

Enrollment/randomization

Screening, recruitment, and enrollment of participants will occur in the obstetrical clinics and on Labor and Delivery at Brigham and Woman's Hospital (BWH), Beth Israel Deaconess Medical Center (BIDMC) and at Massachusetts General Hospital (MGH). Possible eligible patients may be handed a brochure about the study by their OBGYN provider at BIDMC so they can decide make an informed choice about participating. We will review the medical record of potentially eligible patients to confirm eligibility. At the time we approach each patient, we will review the eligibility criteria with the patient to further ensure eligibility. A script is available for the consenter. Specifically, consistent with standard medical care, we will confirm with patients that they do not have a history of allergic reaction to adhesives, such as those used in medical tape.

Participants who meet eligibility criteria and provide written, informed consent will be randomized to the traxi arm or standard of care (control) arm. We will use computer-generated block randomization to randomize participants in a 1:1 ratio to the traxi arm or the control arm. Randomization will be stratified by whether the patient has a history of cesarean delivery / open abdominal surgery versus no history of cesarean delivery / open abdominal surgery versus no history of cesarean delivery.

Study procedures

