After the participant is in the operating room and before the cesarean delivery, we will use a spirometer to measure forced vital capacity, forced expiratory volume, vital capacity and tidal volume. We will perform these measurements while the participant is in the supine position both before any retraction has occurred and after the traxi device or standard method for panniculus retraction has been applied.

After the cesarean delivery is complete, we will assess provider satisfaction by administering a brief questionnaire developed by our research team. The survey will be distributed to personnel involved in

the delivery either on paper or via REDCap.

We will assess participant satisfaction via a survey that will be available either on paper or via REDCap.

We will conduct a medical record review to collect data on the secondary outcomes below that are not available via spirometry or questionnaire.

Outcomes

The primary outcome will be total operative time, time from incision to closure.

Secondary outcomes will include:

- Spirometry: forced vital capacity, forced expiratory volume, vital capacity and tidal volume
- Provider satisfaction
- Participant satisfaction
- Intraoperative data, such as estimated blood loss and number of scrubbed personnel
- Neonatal outcomes, such as Apgar score and NICU admission
- Length of stay postoperatively,
- Maternal complications, such as need for re-admission and wound disruption or infection.

B. Statistical Considerations

Sample Size Justification: Our sample size calculation is based on data from a prior study that reported total operative time (incision to closure) by BMI [7]. In that study, for patients with a BMI \geq 40 the mean total operative time was 55.0 minutes (±26 minutes). We hypothesize that the operative time in the control arm will be similar to that in the prior study and that the mean operative time in the traxi arm will be 45 minutes (±10 minutes). Using a two-sided alpha of 0.05, in order to achieve 85% power to detect the specified difference we will need 102 participants per arm. To allow for 15% loss to follow-up, we will aim to enroll 120 participants per arm.

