We hypothesize that participants will have a baseline forced vital capacity of 2.0L and that after retraction the forced vital capacity will drop by 0.1L to 1.9L in the control am. Assuming a two-sided alpha of 0.05, we will have more than 85% power to detect a difference between the 0.1L decrease in the control arm and a 0.19 L decrease in the traxi arm (assuming a standard deviation of the difference of 0.2L).

Data Analysis: We will employ an intention-to-treat approach for the data analysis. Descriptive data will be presented as a proportion, mean with standard deviation or median with interquartile range. Comparisons will be made using Chi-square or Fisher's exact test for categorical variables and parametric or non-parametric tests for continuous variables based on data distribution.

We will use linear regression to estimate beta and 95% confidence intervals for difference in the primary outcome, time from incision to closure, between the traxi and control arms. While we anticipate that randomization will balance the distribution of measured and unmeasured potential confounders in the two study arms, if this is not the case, we will assess the influence of potential confounders as needed. We will use a similar analytic approach for the secondary outcomes, which also are continuous. All data will be analyzed with SAS 9.4 (SAS Institute Inc., Cary, NC, USA). All tests will be two sided and a P value <0.05 will be required to confer significance.

Release of Data

Data from study participants enrolled at BWH and MGH will be sent to BIDMC, the coordinating site. A data use agreement will be executed to facilitate data transfer. Data will be sent via secure data transfer.

The PI will create a research steering committee that includes the PI and at least one other coinvestigator. All requests to use data from the study must be made in writing and will be reviewed by the steering committee. Release of data may occur after appropriate data use agreements have been enacted.

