Investigators can request to use 1) data that contain elements of a limited dataset or 2) data that are completely de-identified. Investigators who wish to obtain data that contain elements of a limited dataset first must obtain approval from the steering committee and then will have to obtain appropriate approval from the BIDMC Committee on Clinical Investigations (CCI) and from their own institution. After obtaining approval, data may be given to the researchers. Investigators who wish to receive completely de-identified data may do so after approval by the steering committee and after signing a letter indicating that they will not attempt to obtain the identity of any of the participants. A data use agreement or material transfer agreement will be executed as needed.

C. Subject Selection

Inclusion criteria for patients

- Pregnant
- Age 18-50 years
- BMI greater than or equal to 40 kg/m²
- Undergoing non-emergent cesarean delivery
- Able and willing to provide written, informed consent
- Singleton gestation

Inclusion criteria for providers

- Listed as a provider_on the patient's delivery summary
- May include nurse, resident, attending, medical student, anesthesiologist, physician's assistant, surgical technician

Exclusion criteria for patients

- Fetal demise
- Disruption of abdominal skin, such as due to infection, rash, abrasion or laceration
- Known adhesive allergy

B4. POSSIBLE BENEFITS

We do not know whether participants in the study will gain any direct benefit from participation. However, we hope that this study will provide data to inform how we can improve care for future patients. It is possible that participants who are randomized to the intervention arm of this study will have a better delivery experience due to increased preservation of dignity. It also is possible that providers will benefit by improving retraction capability and thus visualization while operating and operative efficiency.

B5. POSSIBLE RISKS AND ANALYSIS OF RISK/BENEFIT RATIO

There are very few anticipated risks involved in this study. Patients with an allergy to adhesives may experience a contact dermatitis allergic reaction to the adhesive of the traxi device or the medical tape.

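### Additional procedures planned before randomization are neither specified as a data item nor adjusted for in the operative-time analysis: a cheap precision gain, with no bias at issue

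*Combined protocol and SAP*

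**What the plan says.** Section B3.A, Outcomes, defines the endpoint: "The primary outcome will be total operative time, time from incision to closure". No part of that interval is set aside.

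Section B3.C, Subject Selection, limits the type of surgery only by "Undergoing non-emergent cesarean delivery". There are three exclusions: fetal demise, a known adhesive allergy, and "Disruption of abdominal skin, such as due to infection, rash, abrasion or laceration". None concerns a second procedure at the same operation.

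Section B3.A, Enrollment/randomization, names surgical history as the only stratification factor: "Randomization will be stratified by whether the patient has a history of cesarean delivery / open abdominal surgery".

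On data collection, Section B3.A lists "Intraoperative data, such as estimated blood loss and number of scrubbed personnel" among the secondary outcomes. The source is given as: "We will conduct a medical record review to collect data on the secondary outcomes below that are not available via spirometry or questionnaire". The list is open-ended, and neither of its two examples is an additional procedure.

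Section B3.B, Data Analysis, sets the primary analysis: "We will use linear regression to estimate beta and 95% confidence intervals for difference in the primary outcome, time from incision to closure". It names no covariate. It expects randomization to balance potential confounders and adds: "if this is not the case, we will assess the influence of potential confounders as needed".

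**The concern.** Some patients will come to the operating room with more than a cesarean planned. Sterilization is the obvious example. The extra minutes are foreseeable from the booking or the consent, before allocation, and they count fully in the outcome. A baseline variable that predicts the outcome can be put in the regression to narrow the confidence interval without disturbing the intention-to-treat comparison.

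The plan's adjustment clause does not do this job. It is triggered by apparent imbalance, whereas the variance from a strong predictor is present even when the arms are perfectly balanced. It also names no variable, so the choice would be made after the data are seen, in an open-label trial. At stake is some precision in the primary comparison, and a primary model fixed in advance.

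**Working it through.** **Inputs from the documents** (Section B3.B, Sample Size Justification): control 55 min, SD 26; traxi 45 min, SD 10; difference 10 min; two-sided alpha 0.05; 102 per arm analysed, for a stated 85% power.

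**Inputs assumed**, because the documents never mention additional procedures: a proportion p = 15-30% of patients in each arm, each adding a fixed m = 10-15 min, unrelated to arm and to the rest of the operating time.

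**Step 1. The plan's own figure.** With unequal SDs the standard error is √((26² + 10²)/102) = √(776/102) = 2.76 min. The Welch t-test then has 94.9% power at 102 per arm. The stated 85% would need 72 per arm, so 102 does not reproduce as an 85% figure. That is a separate matter. Here it means the starting point under the stated SDs is 94.9%. If the traxi SD were also 26, the standard error would be √(2 × 676/102) = 3.64 min and power 78.0%.

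**Step 2. Variance contributed.** A yes/no procedure adding m minutes contributes p(1 − p)m².

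| p | m (min) | Variance (min²) | Share of 26² = 676 |
|---|---|---|---|
| 0.15 | 10 | 12.75 | 1.9% |
| 0.20 | 10 | 16.0 | 2.4% |
| 0.20 | 15 | 36.0 | 5.3% |
| 0.30 | 15 | 47.25 | 7.0% |

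Against the assumed traxi variance of 10² = 100, the range is 13-47%.

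**Step 3. Power if this variance is already in the planning SDs and adjustment removes it from both arms.**

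| Removed (min²) | SE, SDs 26 and 10 | Power | SE, SD 26 in both | Power |
|---|---|---|---|---|
| 0 | 2.76 | 94.9% | 3.64 | 78.0% |
| 12.75 | √((663.25 + 87.25)/102) = 2.71 | 95.5% | √(2 × 663.25/102) = 3.61 | 78.8% |
| 47.25 | √((628.75 + 52.75)/102) = 2.58 | 97.0% | √(2 × 628.75/102) = 3.51 | 80.9% |

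**Step 4. Power if the variance instead comes on top of the stated SDs.** Without adjustment the standard error rises to √((688.75 + 112.75)/102) = 2.80 or √((723.25 + 147.25)/102) = 2.92, and power falls from 94.9% to 94.3% or 92.5%. Adjustment would restore it to about 94.9%.

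**Step 5. Chance imbalance.** One SD of the shift in the estimated difference is m√(2p(1 − p)/102). This is 10 × √(0.255/102) = 0.50 min at the low end and 15 × √(0.42/102) = 0.96 min at the high end, against a 10-minute target. When the variance is already in the SDs, this shift is part of the standard error in Step 3 and not a further loss.

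**The case against.** The strongest reply is that this is an efficiency suggestion of unverifiable size. Every frequency and duration is assumed. The SD of 26 comes from incision-to-closure times in a prior study and may already contain such procedures, in which case the sample size allows for them. Under the plan's own SDs power is already near 95%, so little is left to gain. All of this stands, and it sets the priority.

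The outcome itself is also defensible. The Overview asks whether the device belongs in routine practice, and whole-operation time among all non-emergent cesareans fits that question. Better retraction might also shorten work done through the same incision, so the extra time cannot be assumed irrelevant to the device.

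Four stronger readings are tempting, and the documents do not support them:

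- **That the treatment effect is biased or contaminated.** Procedures planned before 1:1 randomization are independent of arm.
- **That nothing will record or model these procedures.** The intraoperative list is open-ended and the confounder clause permits later adjustment. What is missing is a specification.
- **That a few very long planned operations could dominate the result.** If 1-2% of patients had a planned hysterectomy adding 60 minutes (also assumed), one SD of chance shift would be 60 × √(2 × 0.01 × 0.99/102) = 0.8 min to 60 × √(2 × 0.02 × 0.98/102) = 1.2 min, against 10.
- **That planned hysterectomy should therefore be excluded.** That would narrow the population of a pragmatic trial for little return.

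The reply does not show that the adjustment clause is an adequate substitute. It is conditional, names no variable and does not address precision when the arms are balanced.

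**Conclusion.** The omission is real and minor. The plan specifies neither a record of, nor an adjustment for, additional procedures already planned before randomization, and so leaves predictable variance in the primary comparison. The estimate remains unbiased and the endpoint does not need to change.

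On the assumed values, adjustment is worth 0.6 to 2.1 percentage points of power under the stated SDs (95.5 − 94.9 and 97.0 − 94.9), and 0.8 to 2.9 points if the SD is 26 in both arms (78.8 − 78.0 and 80.9 − 78.0). The upper end for the stated SDs assumes that nearly half of the traxi arm's variance of 100 comes from these procedures, which is generous. The case for the change rests on its very low cost and on fixing the primary model in advance.

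**What to change.** At enrollment, before randomization, record from the surgical booking or consent whether an additional procedure is planned: none, sterilization or other. In Section B3.B, name this variable as a covariate in the primary linear regression, to be included whether or not the arms look balanced.

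Keep patients who have unplanned additional procedures in the intention-to-treat analysis without adjusting for those procedures, because they arise after allocation. Leave the exclusion criteria as they are.

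The cost is one data item, which staff can collect during the medical record review already done to confirm eligibility, and one model term. No change in recruitment is needed.

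### The stated 85% power at 102 per arm follows neither from the printed SDs (26 and 10, which give about 95%) nor from an SD of 26 in both arms (78%), and the traxi-arm SD of 10 has no source

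*Combined protocol and SAP*

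**What the plan says.** Section B3.B (Statistical Considerations, Sample Size Justification) takes the control assumption from a prior study: "for patients with a BMI \geq 40 the mean total operative time was 55.0 minutes (±26 minutes". It carries this over to the control arm: "We hypothesize that the operative time in the control arm will be similar to that in the prior study". For the device arm it supposes that "the mean operative time in the traxi arm will be 45 minutes (±10 minutes", and it gives no citation, pilot data or reason for the 10. The conclusion is: "Using a two-sided alpha of 0.05, in order to achieve 85% power to detect the specified difference we will need 102 participants per arm". An allowance of 15% for loss raises the target to 120 per arm. No other SD is tried.

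Two other places bear on this. The background in section B2 says that primary data on the device are lacking. The prior study is cited as reference 7, but section B2 and its reference list use number 7 for the registry record of a trial that ended after four subjects.

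**The concern.** The device arm is given an SD less than half that of the control arm, with no data behind it. Both arms are randomized 1:1 from the same three hospitals, with stratification on surgical history, so they should share the same mix of patients. The protocol gives no reason why the retractor should remove most of the spread in operative time.

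Power for the primary outcome depends directly on this SD. A reader of the final report needs to know how large a chance the trial had of detecting 10 minutes, above all if the result is not significant. There is also a practical risk. Someone who re-runs the calculation on the printed inputs will get a much smaller number than 102 and may conclude that the target can be cut.

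**Working it through.** **Inputs**, all from section B3: difference 55 − 45 = 10 minutes; control SD 26; traxi SD 10; two-sided alpha 0.05; power 85%; 102 per arm; 15% loss; 1:1 allocation. The ± is read as an SD, which the protocol does not define.

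**Formulas** (two-sample comparison of means):
- n per arm = (SD₁² + SD₂²)(z₀.₉₇₅ + z_power)² / difference²
- power = Φ(difference / SE − 1.960), with SE = √((SD₁² + SD₂²)/n)

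**1. The plan's figure from its own inputs.** SD₁² + SD₂² = 676 + 100 = 776.
- For 85% power: 776 × (1.960 + 1.036)² / 100 = 69.7, so 70 per arm, or 71 with the t distribution. The plan says 102.
- At 102 per arm: SE = √(776/102) = 2.758; 10/2.758 − 1.960 = 1.666; power 95.2% (95.0% by t test). The plan says 85%.
- For 95% power: 776 × (1.960 + 1.645)² / 100 = 100.8, or 101.8 by t test, which rounds up to 102.

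So 102 fits the printed SDs at 95% power, not at 85%.

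**2. Other routes to 102 at 85% power.** None of these gives 102:

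| Variant | n per arm |
|---|---|
| One-sided alpha, SDs 26/10 | 56 |
| One-sided alpha, SDs 26/26 | 98 |
| Two-sided alpha, SDs 26/26 | 122 |
| Both SDs set to the mean, 18 | 59 |
| SDs 26/10, inflated for a rank test | 73 to 81 |

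Working backwards, 102 at 85% needs a common SD of about 23.8, or a traxi SD of about 21.4 beside a control SD of 26. The plan prints neither value.

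**3. The loss allowance.** 102/0.85 = 120. This reproduces.

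**4. What an SD of 10 implies.** 1 − 100/676 = 0.852, so 85% less variance than in the control arm.

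**5. Power over a range of traxi SDs**, with control SD 26 and difference 10. The range is an assumption.

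| Traxi SD | n per arm | SE | Power (normal) | Power (t test) |
|---|---|---|---|---|
| 10 | 102 | 2.758 | 95.2% | 95.0% |
| 15 | 102 | 2.972 | 92.0% | 91.8% |
| 20 | 102 | 3.248 | 86.8% | 86.5% |
| 21.3 | 102 | 3.326 | 85.2% | 84.9% |
| 26 | 102 | 3.641 | 78.4% | 78.0% |
| 26 | 120 | 3.357 | 84.6% | 84.3% |

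The value 21.3 is 26 × 45/55, the SD if traxi shortens every operation in the same proportion. With SD 26 in both arms, 85% power needs 122 per arm (123 by t test).

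**6. If the target were cut on the printed inputs.** At 71 per arm with SD 26 in both arms, SE = √(1352/71) = 4.364, and power is 63% (62% by t test).

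**The case against.** The strongest reply is that the plan is not optimistic. For its printed SDs, 85% understates the power of 102 per arm, and 102 keeps about 85% up to a traxi SD of about 21. A proportional saving, a reasonable model for durations, gives almost exactly that SD. The figure of 78% needs a pure shift with no loss of spread, and it also needs the full 15% loss. Operative time runs from incision to closure and is recorded during the delivery, so the actual loss may be small. With all 120 per arm evaluable, even SDs of 26 and 26 give 84%. The 26 may not carry over either: the trial takes only non-emergent singleton cesareans, and the documents do not say whether the prior group was restricted in this way.

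All of this stands. It limits the shortfall to traxi SDs above about 21 and rules out 78% as the single headline. It does not supply a source for the 10 or make the printed figures agree.

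Three stronger readings are tempting, and none is supported:
- **That the low SD of 10 is what yields the stated 85%.** It is not: that SD gives 95% at 102 per arm.
- **That SDs of 26 and 10 with a mean saving of 10 force about 27% of patients to have longer operations.** This follows only under normality: the individual effects would need an SD of at least 26 − 10 = 16, and Φ(−10/16) = 0.27. If times are right-skewed and the device mainly shortens long cases, it fails. Capping a lognormal with mean 55 and SD 26 so that its mean is 45 gives an SD of about 11, with nobody longer.
- **That the planned linear regression shows the SDs to be equal.** With equal arm sizes the pooled and unequal-variance standard errors coincide, so the choice of model says nothing about the SDs.

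**Conclusion.** The point holds as an inconsistency together with an unsupported input. On the printed SDs the power at 102 per arm is 95%, ten points above the stated 85%. With the only SD that the plan attributes to data used in both arms, it is 78%, seven points below. The stated figure is right only for a traxi SD of about 21, which the plan does not mention.

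The documents do not support the conclusion that the trial is underpowered. They support a range of 78% to 95% at 102 evaluable per arm, with 84% as the low end if all 120 per arm are evaluable. How 102 was obtained cannot be told from the text. Its match with 95% power on the printed SDs may be coincidence.

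This rests on reading ± as SD, a true difference of 10 minutes, a control SD of 26, and a traxi SD between 10 and 26. The 26 is itself only as good as its citation. Reference 3, whose title concerns BMI and operative times at cesarean delivery, looks like the intended source, but the sponsor must confirm this.

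**What to change.** Reword the sample-size paragraph in section B3.B:
- Reconcile 102, 85% and the two SDs, and say which inputs produced 102.
- Give a reason for the traxi SD of 10, or label 26/10 as the optimistic case.
- Replace the single 85% with a range. For example, at 102 evaluable per arm, power to detect 10 minutes with a control SD of 26 is 95%, 87%, 85% or 78% for a traxi SD of 10, 20, 21 or 26. With all 120 per arm evaluable and SD 26 in both arms, it is 84%.
- Keep enrolment at 120 per arm, and do not lower it on the strength of the 26/10 inputs.
- Correct the citation for the SD of 26, and state that ± denotes an SD.

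The cost is one paragraph and one reference number. No extra patients are needed and the analysis does not change. The drawback is that the stated power may become less favourable than 85%.

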Obesity rates have reached an all-time high in the general U.S. population. Currently, it is estimated that 25.6% of pregnant people have a BMI >30 and are considered obese [1]. Studies have shown that obese pregnant people are at higher risk for cesarean delivery and that their risk increases proportionately with increased BMI [2]. From a provider perspective, performing a cesarean delivery on an obese individual can be more technically challenging given the need for panniculus retraction to facilitate visualization of vital anatomic structures and delivery of the infant. As a result, operative times can be longer and additional personnel may be required in the operating room to assist in the delivery [3]. In addition, vital capacity has been shown to be drastically reduced in obese pregnant patients, as compared to non-obese pregnant patients [5,6].

The traxi® panniculus retractor (Clinical Innovations, Murray, UT) is designed to reliably retract the panniculus during surgery, thereby reducing the need for extra personnel for retraction; improve visualization to decrease operating time; and improve patient satisfaction with the delivery experience by preserving patient dignity. While the producers of this device claim that traxi is associated with these improved outcomes, no clinical trials exist to support these claims. A single clinical trial was initiated but was terminated due to low enrollment with only four subjects [7]. Given the absence of primary data in support of this device, we propose this clinical trial to examine traxi's utility and potential benefits to this patient population.

References

- Chu, S. Y., Kim, S. Y., Schmid, C. H., Dietz, P. M., Callaghan, W. M., Lau, J. and Curtis, K. M. (2007), Maternal obesity and risk of cesarean delivery: a meta-analysis. Obesity Reviews, 8: 385–394.
- 4. Poobalan, A. S., Aucott, L. S., Gurung, T., Smith, W. C. S. and Bhattacharya, S. (2009), Obesity as an independent risk factor for elective and emergency caesarean delivery in nulliparous women systematic review and meta-analysis of cohort studies. Obesity Reviews, 10: 28–35.

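### The stated 102 per arm and 85% power do not belong together: the protocol's inputs need about 71 per arm for 85%, and 102 per arm gives 95%

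*Combined protocol and SAP*

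**What the plan says.** Section B3.B, Sample Size Justification, sizes the trial on total operative time from incision to closure. For the control arm it takes over a prior study's result at BMI 40 or above, where "the mean total operative time was 55.0 minutes (±26 minutes". For the intervention arm it hypothesises that "the mean operative time in the traxi arm will be 45 minutes (±10 minutes". The error rate is given by "Using a two-sided alpha of 0.05", and the conclusion is that "in order to achieve 85% power to detect the specified difference we will need 102 participants per arm". An allowance of 15% for loss to follow-up raises this to 120 per arm. Section B3.A sets 1:1 allocation.

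Under Data Analysis in the same section, the primary analysis is described as follows: "We will use linear regression to estimate beta and 95% confidence intervals for difference in the primary outcome". The significance rule is "All tests will be two sided and a P value <0.05 will be required to confer significance". A second power statement, for forced vital capacity, rests on the same sample size: "we will have more than 85% power to detect a difference between the 0.1L decrease in the control arm". The comparison is with an assumed fall of 0.19 L under traxi, and the SD is taken as 0.2 L.

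**The concern.** Every input that a two-sample comparison of means needs is printed, so the sample size should follow from them. It does not: 102 is well above what 85% power requires. No test, formula, common SD, rank-test inflation or multiplicity adjustment is named that would account for the difference.

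This sentence is the only derivation of 102 and hence of the enrolment target of 120. As printed, it tells the reader that the risk of missing a true 10-minute difference is 15%, whereas the printed inputs give 5%. If 85% is what was meant, then an SD, the alpha or the method is misreported, and the reader cannot tell which.

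**Working it through.** **Inputs (section B3.B unless noted).** Control 55 minutes, SD 26. Traxi 45 minutes, SD 10. Difference 10 minutes. Two-sided alpha 0.05. Power 85%. Allocation 1:1 (section B3.A). The ± values are read as SDs; the protocol does not label them.

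**1. The attrition step reproduces.** 102 / (1 − 0.15) = 120 per arm. The discrepancy is therefore in the 102 itself.

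**2. Sample size for 85% power, normal approximation.**

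n per arm = (SD₁² + SD₂²) × (z for alpha + z for power)² / difference²

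= (26² + 10²) × (1.960 + 1.036)² / 10² = 776 × 8.978 / 100 = 69.7, so 70 per arm.

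**3. The same with t tests.** The root-mean-square SD is √(776/2) = 19.70, so the standardised difference is 10 / 19.70 = 0.508. With noncentral-t power, the equal-variance test needs 71 per arm (70 gives 84.7%, 71 gives 85.2%). The Welch test needs 72.

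**4. Power at 102 per arm.** The standard error is √(776/102) = 2.758 and 10 / 2.758 = 3.626. The normal approximation gives Φ(3.626 − 1.960) = 95.2%. The equal-variance t test gives 95.0% and Welch 94.9%. A simulation of 100,000 trials gave 95.1%.

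**5. Can 102 be recovered?** All rows use a 10-minute difference.

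| Variant | n per arm | Conflict with the text |
|---|---|---|
| Stated SDs, two-sided 0.05, 85% | 70 (z), 71 (t), 72 (Welch) | none |
| Stated SDs, two-sided 0.05, 95% | 101 (z), 102 (t), 103 (Welch) | power is stated as 85% |
| Stated SDs, two-sided 0.01, 85% | 102 (z), 103 (t), 104 (Welch) | alpha is stated as 0.05 |
| SD 26 in both arms, two-sided 0.05, 85% | 122 (z), 123 (t) | traxi SD is stated as 10 |
| SDs averaged to 18, two-sided 0.05, 85% | 59 (z) | not the SDs stated |
| Stated SDs, one-sided 0.05, 85% | 56 (z) | alpha is stated as two-sided |
| Stated SDs, 85%, divided by a rank-test efficiency of 0.864 | 82 (z) | no such inflation is stated |

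The equal-variance t test, which is what an unadjusted linear regression on arm amounts to, needs exactly 102 for 95% power (101 gives 94.8%). A 95% calculation reported as 85% is therefore one simple explanation. The alpha 0.01 route is another. The protocol does not identify either.

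**6. Forced vital capacity.** The difference is 0.19 − 0.10 = 0.09 L with SD 0.2 L, a standardised difference of 0.45. The equal-variance t test needs 90 per arm for 85% power. Power is 89% at 102 per arm and 76% at 71.

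**7. Dependence on the traxi SD.** The values of 15, 20 and 26 below are assumptions, with a 10-minute difference and control SD 26.

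| Traxi SD | Power at 102 per arm | Power at 120 per arm |
|---|---|---|
| 10 (stated) | 95% | 97% |
| 15 | 92% | 95% |
| 20 | 87% | 91% |
| 26 | 78% | 84% |

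**The case against.** The strongest reply is that the consequence is small. The error makes the trial larger than 85% power requires, and correcting it changes neither enrolment, analysis nor alpha. That stands, and it is why the point calls for a text correction and not a redesign.

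A second reply is that 102 may contain a deliberate allowance for skewed operative times or a rank test. Data Analysis does allow non-parametric tests in general, but it names linear regression for the primary outcome. The usual worst-case rank-test inflation reaches only 82, and the only inflation stated is the 15% for attrition.

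Third, the origin of 102 is conjecture. This also stands. The 95% explanation hits 102 exactly only with the equal-variance t test, and the alpha 0.01 explanation only with the normal approximation. The correspondence with linear regression holds for the unadjusted model, while the plan leaves confounder assessment open. The mismatch does not depend on any of this.

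Fourth, the sensitivity figures rest on SDs that are not in the protocol. They are not needed to establish the error; they show only how far the 95% depends on the traxi SD of 10.

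**Conclusion.** The concern holds. On the printed inputs, 85% power needs 70 to 72 per arm and not 102, and 102 per arm gives 95% power and not 85%. This assumes that ± denotes an SD and that the arms are compared by a two-sample test of means or its unadjusted regression equivalent. The choice among the normal approximation, equal-variance t and Welch moves the answer by only two participants per arm.

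The trial is not underpowered on its own assumptions. The 95% does rest on the traxi SD of 10, for which no source is given. With control SD 26, power at 102 per arm falls below 85% once the traxi SD exceeds about 21. If both SDs are 26 it is 78%, or 84% if all 120 per arm are analysed.

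**What to change.** Keep the target of 120 per arm. In the Sample Size Justification, state the test, alpha and SDs that produced 102, say that ± means SD, and correct whichever figure is wrong. If no other input was used, the sentence could read: *With a two-sided alpha of 0.05, 102 evaluable participants per arm give 95% power to detect a difference between 55 (SD 26) and 45 (SD 10) minutes (two-sample t test).*

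Do not reconcile the text by lowering 102 to 71. The forced vital capacity claim of more than 85% power would then fail.

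One further line, labelled as an assumption, would be useful: with control SD 26 and 102 per arm, power is 92%, 87% and 78% for traxi SDs of 15, 20 and 26.

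Also check the citation for the SD of 26. It is given as reference 7, which section B2 uses for a different purpose: "A single clinical trial was initiated but was terminated due to low enrollment with only four subjects [7". By its title, reference 3, on body mass index and operative times at cesarean delivery, looks the more likely source, so this may be a numbering slip.

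The cost is protocol wording, with no change to enrolment or analysis. The downside is that the sensitivity line shows openly that power could fall below 85% if both SDs are 26.
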